13.2 Off-Schedule Evaluations

Patient's returning for an AE will have an evaluation by the study coordinator and PI and an adverse event form will be filled out. Further evaluation for clinical care of the patient will be performed appropri-

ate to the care of the patient and the nature of the AE event. No other evaluations specific to the study will be performed.

13.3 Evaluations for Drop-Outs and Withdrawals

If a subject drops out of the study for any reason, the subject will be encouraged to complete as many of the study procedures as they will agree to as outlined in section 13.1 above.

14. OUTCOME DETERMINATIONS

14.1 Primary Outcome: Maximal oxygen uptake (peak VO₂) at cardiopulmonary exercise testing (CPXT).

For baseline or screening CPXT, the CPXT may be done at any time in the evaluation process. For studies on therapy (12 and 24 weeks), study patients should take their study medication on site approximately 1 hr (45-120 minutes) prior to blood draw for study labs. CPXT should be performed immediately after the blood draw. All screening CPXT should be performed using the same protocol as is used for baseline and follow up CPXT in RELAX and may be used as the baseline CPXT.

Cardiopulmonary exercise testing (CPXT) will be performed using the best exercise modality, determined by the CPXT lab and the patient. The chosen exercise modality should be used for all subsequent CPXT tests. Please see the Cardiopulmonary Exercise Testing Manual of Operating Procedures for details regarding the methods to be used during the CPXT.

A number of other exercise variables will be recorded to allow further post hoc exploratory analyses including time to ventilatory anaerobic threshold, VO2 max at ventilatory anaerobic threshold, and oxygen uptake efficiency slope⁹⁵.

14.2 Secondary and Tertiary Outcomes

14.2.1 Composite Clinical Score

A composite clinical score in RELAX will be based on a ranking of all participants. All participants will be ranked sequentially with ranking stratified in one of three tiers based on:

1) Death (lowest tier)

The ranking within this tier is based on time to death from randomization date. The person with the shortest time from randomization to death is given the lowest rank within the tier.

2) Hospitalizations due to cardiovascular (CV) or renal causes (middle tier)

For patients alive, the ranking within this tier is based on time to hospitalization from randomization date. The person with the first cardiovascular or renal cause hospitalization will be given the lowest rank within the tier. Cardiovascular causes defined as initial primary cause for hospitalization as HF, acute coronary syndrome, cerebrovascular accident, peripheral vascular disease, arrhythmia or syncope. Renal causes defined as initial primary cause for hospitalization, renal failure or hyperkalemia.

3) Change in MLWHFQ from baseline (highest tier)

For patients without an event meeting the first two criteria, the person with the least favorable change in MLWHFQ is given the lowest rank within this tier. Patients with an equal change in the MLWHFQ will receive an equal ranking.

The use of three tiers within the ranking reflects the greater adverse impact of death or CV hospitalization on clinical status without an arbitrary assignment as to the relative value of these events in relation to changes in quality of life.

14.2.2 Minnesota Living with Heart Failure Questionnaire:

The MLWHFQ is a self-administered, disease-specific measure of health related quality of life (QOL) that assesses patients' perceptions of the influence of HF on physical, socioeconomic and psychological aspects of life⁹⁶⁻⁹⁸. Patients respond to 21 items using a six-point response scale (0-5). The total summary score can range from 0-105 with a lower score reflecting better HF related QOL. Two subscale scores reflect physical (8 items) and emotional (5 items) impairment. This instrument has been extensively validated and widely used to assess treatment effect on clinical status in multiple trials of therapeutic interventions in HF.

14.2.3 Six minute hall walk

The six minute walk test is widely used to assess submaximal exercise performance in clinical trials conducted in patients with HF or pulmonary disease. Use of the six minute walk test as an outcome measure in randomized, blinded intervention trials of chronic HF has been comprehensively reviewed⁹⁹ and its use in elderly patients with HF has been specifically reviewed¹⁰⁰.

Six minute walks will be performed by registered RN or LPN study coordinators or trained exercise technicians using a standardized approach using a 25 meter course in an enclosed corridor with a chair placed at each end of the course. Patients will be allowed to use any mobility aids they traditionally use Patients will be instructed to walk from end to end at their own pace while attempting to cover as much ground as possible in the six minutes using a standardized script.

"The purpose of this test is to find out how far you can walk in six minutes. You will start from this point and walk back and forth between the two markers I showed you. You will go back and forth as many times as you can in the six-minute period. If you need to, you may stop and rest. Just remain where you are until you can go again. However, the most important thing about the test is that you cover as much ground as you possibly can during the six minutes. I will tell you the time, and I will let you know when the six minutes are up. When I say 'stop', please stand right where you are."

During the walk, the following words of encouragement will be provided at 30-second intervals "...you're doing well"..."keep up the good work"..."good job"..."you're doing fine".

The patient will be notified when 2, 4, and 6 minutes (stop) have elapsed and what the remaining time is. Patients will be allowed to slow or stop and rest during the walk but will be asked to resume walking as soon as they feel able. After six minutes, the distance walked will be measured to the nearest meter. Vital signs (heart rate and blood pressure) will be obtained before and immediately after the test in the standing position. Patients will indicate symptoms limiting ability to walk during the test (dyspnea, fa-tigue, chest pain, leg or joint pain, instability, other, none).

14.2.4 Cardiac MRI for assessment of LV and vascular structure and function

Patients in atrial fibrillation will not undergo baseline or follow-up MRI. Patients will undergo cardiac MRI for measurement of LV end diastolic volume, LV end systolic volume, LV mass, ascending aortic wall thickness and ascending aortic maximal and minimal cross sectional area (CSA). Systolic (SBP) and diastolic (DBP) blood pressure and heart rate will be assessed at the time of aortic imaging using a non-ferromagnestic sphygmomanometer. LV volumes and LV mass will be calculated according to Simpson's rule on traced endocardial and epicardial short axis LV images. Aortic wall thickness will be measured along the wall of the aorta adjacent to the superior vena cava in a region free of atheroscle-rotic plaque. Derived indices of ventricular and aortic function will include:Ejection fraction (%) = [(LV end diastolic – end systolic volume)/LV end diastolic volume] x 100%; Stroke volume (mI) = (LV end diastolic – end systolic volume); Aortic distensibility (10^{-3} mmHg) = (aortic CSA_{max} – aortic CSA_{min})/(aortic CSA_{min} x (SBP-DBP)); Effective arterial elastance (Ea, mmHg/mI) = (SBP x 0.9)/stroke volume; systemic vascular resistance (dyne*sec/cm⁵) = 80 x [MAP/(stroke volume x heart rate)]

EKG gated MRI images will be obtained using a phased-array cardiac surface coil placed on the chest. After initial localization scans, short axis cine images 8 mm thick with a 2 mm gap will be obtained perpendicular to the long axis of the ventricle scanning from base to apex using a steady state free precession fast gradient echo sequence (fiesta) with the following parameters: TE min full, flip angle 45°, bandwidth 125 kHz, matrix 256x192-224, field of view 34-40 cm, 20 cardiac phases, 12 views per segment, and number of acquisitions 0.5-1.0. Each short axis slice typically requires 10-15 seconds to acquire depending on the heart rate, and parameters (matrix, views per segment, and number of acquisitions) will be adjusted on an individual basis according to heart rate and breath hold capacity. Using a mid ventricular short axis cine image, long axis views with the same parameters will be prescribed perpendicular to the plane of the ventricular septum.

Cardiac cycle-dependent changes in the aortic lumen will be assessed as previously described ^{32,50} with interleaved, velocity encoded, phase-contrast, gradient echo images acquired perpendicular to the course of the proximal ascending thoracic aorta approximately 4 cm above the aortic valve. Scans will have slices 6 mm thick with a 256 x 256 matrix, a 26 cm field of view, a 40° flip angle, an 11 ms repetition time, a 3.5 ms echo time and a through-plane velocity encoding of 150 cm/s.

To assess aortic wall thickness, double inversion recovery fast spin echo images will be acquired in the same slice position as that used to assess aortic distensibility. These scans will have an echo train length of 32, a repetition time of 2 x the R-R interval, a 650 ms inversion time, a 42 ms echo time, a 30 cm field of view and a 256 x 256 matrix 32,50 .

Images will be transferred to a windows workstation and an appropriate software analysis package will be used to analyze images at a core MRI laboratory. The average of two measurements will be used for each parameter.

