12. BASELINE EVALUATIONS AND RANDOMIZATION

12.1 Evaluations Performed During the Baseline Period

The following studies will be performed during the baseline period prior to randomization and starting study drug. Please see section 13 for a detailed description of these procedures as well as the schedule of evaluations as outlined in Appendix 22.1.

- 1. Limited Doppler echocardiography
- 2. Cardiac Magnetic Resonance Imaging (MRI) (Patients in sinus rhythm only at enrolling sites with MRI access)
- 3. Phlebotomy for Biomarkers
- 4. Metabolic stress test (Screening study may be submitted to the CORE CPXT laboratory as the baseline study if patient meets entry criteria)
- 5. Six minute walk test
- 6. Minnesota Living with Heart Failure Questionnaire
- 7. Creatinine
- 8. Electrocardiogram
- 9. Clinical history
- 10. Physical examination which will include simple bedside hearing assessment (ability to hear examiner's fingers rubbed together in front of each ear).

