14.2.5 Doppler echocardiography

A limited 2 D, M-mode and Doppler echocardiogram will be performed in each subject in the left lateral (parasternal long axis view and right ventricular (RV) inflow view) and the left lateral decubitus (apical 4 chamber and long axis views) positions using an appropriate echocardiographic instrument equipped with a multifrequency transducer as well as the Doppler tissue imaging (DTI) program. Blood pressure and heart rate will be recorded after the patient has acclimated to the imaging environment. In the parasternal long axis view, the diameter of left ventricular outflow tract (LVOT) will be measured just below the aortic valve. In the RV inflow view, guided by color flow imaging, continuous wave Doppler imaging will be used to measure the peak tricuspid regurgitant velocity. In the apical long axis view, pulsed wave Doppler echocardiography will be used to measure the LVOT velocity profile. In the apical 4-chamber view, the transmitral inflow velocity profile obtained from pulsed wave Doppler imaging at the tips of the mitral valve will be obtained. Doppler tissue imaging will be used to measure the septal and lateral mitral annular velocity in diastole. Guided by color flow imaging, continuous wave Doppler imaging will be used to measure the peak tricuspid regurgitant velocity. Measurements and derived values will be obtained in triplicate and measurements made at a core echocardiographic laboratory. Measurements and derived values include:

Stroke volume = $[3.14 \text{ x} (\text{LVOT diameter/2})^2]$ x time velocity integral of the pulsed wave LVOT velocity profile

Cardiac output = SV * heart rate

E velocity (cm/s) from the transmitral inflow velocity profile measured at leaflet tips.

E' velocity (cm/sec) (septal and lateral) from the diastolic mitral annular velocities measured with DTI. The E/E' ratio (septal and lateral) will be calculated for each subject.

Operant Ed will be calculated as (E/E')/stroke volume as previously reported ²⁷.

Peak pulmonary systolic pressure = $(4^{*}(\text{Peak TR velocity in m/sec})^{2} + 10)$ using the maximal TR velocity consistently measured (not following extrasystole)

Standardized image acquisition and measurement algorithms along with training materials will be provided to each participating center to enhance standardization of Doppler echocardiographic measurements.

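### The SVR formula in 14.2.4 is 1000 times too small for its stated unit, and Ea and SVR have formulas only under MRI although the echo done in each subject records every input

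*Protocol*

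**What the plan says.** Endpoint 6 (Executive Summary and section 6) is the 24-week change in peripheral vascular function: Ea, SVR, and aortic thickness and distensibility. It names no imaging method and no rhythm restriction.

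The formulas stand in section 14.2.4, among the indices derived from MRI. Stroke volume is defined there in ml ("Stroke volume (mI) = (LV end diastolic", less end-systolic volume). Ea, in mmHg/ml, and SVR then follow in one run: "SBP x 0.9)/stroke volume; systemic vascular resistance (dyne*sec/cm⁵) = 80 x [MAP/(stroke volume x heart rate", with no conversion of units.

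The same section states: "Patients in atrial fibrillation will not undergo baseline or follow-up MRI". Section 12.1 narrows baseline MRI further: "Patients in sinus rhythm only at enrolling sites with MRI access". Sections 8.3 and 18.3 plan for up to 58 patients with chronic atrial fibrillation and allow that limit to be raised after review.

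Section 14.2.5 describes a limited echocardiogram in each subject. It is scheduled at baseline and week 24 (12.1, 13.1, Appendix 1). There, "Blood pressure and heart rate will be recorded after the patient has acclimated to the imaging environment". Stroke volume comes from the outflow-tract diameter and velocity integral, and "Cardiac output = SV * heart rate". Neither Ea nor SVR appears among the echo-derived values.

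**The concern.** There are two separate points.

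First, the SVR expression is the rule from which an endpoint would be computed. If it is programmed as printed, every SVR value and every treatment difference in SVR is mislabelled by three orders of magnitude.

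Second, section 18.1.1 says that the trial is meant to explore mechanisms, and section 5.2 puts peripheral vascular function among them. With formulas given only under MRI, the protocol as written yields Ea and SVR only in sinus-rhythm patients at MRI sites, although the endpoint carries no such limit. The inputs for the remaining patients are already collected by echo.

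**Working it through.** **SVR unit check.** With 1 mmHg = 1333.22 dyn/cm² and 1 l/min = 1000/60 cm³/s, the constant that turns mmHg per unit flow into dyne*sec/cm⁵ is:

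- flow in l/min: 1333.22 x 60/1000 = 79.99, i.e. 80
- flow in ml/min: 1333.22 x 60 = 79,993, i.e. about 80,000

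Stroke volume in ml times heart rate is ml/min, so the printed formula is short by a factor of 1000. The values below are illustrative assumptions, not protocol figures:

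| MAP (mmHg) | Stroke volume (ml) | Heart rate (bpm) | As printed | With flow in l/min |
|---|---|---|---|---|
| 95 | 70 | 70 | 80 x 95/4900 = 1.55 | 80 x 95/4.9 = 1551 |
| 80 | 50 | 60 | 80 x 80/3000 = 2.13 | 80 x 80/3.0 = 2133 |
| 110 | 90 | 80 | 80 x 110/7200 = 1.22 | 80 x 110/7.2 = 1222 |

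The ratio is 1000 whatever the inputs. It is a constant multiplier, so test statistics, p-values, percent changes and standardised effects do not move. The Ea formula is consistent with its unit, because mmHg divided by ml is mmHg/ml.

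**Inputs available from echo.** Ea needs systolic pressure and stroke volume. SVR needs MAP and cardiac output. Section 14.2.5 provides stroke volume, cardiac output, blood pressure and heart rate. MAP has no formula in either section, but follows from systolic and diastolic pressure under any stated convention. Section 14.2.5 prints no unit for stroke volume or cardiac output, so the unit must be named there too.

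**The plan's own precision statement.** Section 18.1.4 claims 85% power at effect size 0.44 for the other tertiary endpoints, with 215 patients and 10% missing. Taking two-sided 0.05 and 1:1 allocation, power = Φ(0.44 x √N/2 − 1.96). At N = 215 x 0.9 = 193.5 this gives 86.4%, so the statement reproduces. It presumes nearly the whole trial. For MRI only, removing 58 patients and keeping 10% missing gives N = 157 x 0.9 = 141.3 and power 74.4%.

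**Gain from echo, like for like.** With equal SD and equal missingness, the ratio of standard errors is √(n MRI / n all):

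- 132 sinus rhythm (18.1.4) against 132 + 58 = 190: √(132/190) = 0.834, a fall of 17%; break-even SD ratio 1/0.834 = 1.20
- 215 − 58 = 157 against 215: √(157/215) = 0.855, a fall of 15%; break-even 1/0.855 = 1.17

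Sites without MRI would lower the MRI count further, but the protocol gives no number for them, so none is used.

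**The case against.** The strongest case against is this. Endpoint 6 names no method, whereas other endpoints do: LV mass by MRI, and diastolic function and pulmonary pressure by Doppler. The echo list is introduced as inclusive, not closed. Echo-based Ea and SVR are arithmetic on collected data, and an analysis plan, which section 18.2 promises, could add them. Taking Ea, SVR, distensibility and wall thickness from one scan, with blood pressure measured at that scan, is coherent. The only comparison of methods in the protocol (18.1.4, for LV mass) favours MRI reproducibility over echo. The SVR error is a unit slip that anyone seeing values near 1.5 would notice. All of this concerns a tertiary endpoint.

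Much of it stands, and it rules out several stronger readings that a reader might infer:

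- That atrial fibrillation patients are lost for Ea and SVR. They are not, because their inputs are recorded. What is missing is a stated derivation.
- That 58 or more patients are affected. The text sets 58 as a cap that may be raised, not a floor.
- That echo cuts the standard error by 26%, with break-even at an SD ratio of 1.35. Those figures come from √(106/194) = 0.739, which sets 132 less 20% against 215 less 10%. They mix bases and missing-data rates.
- That echo should replace MRI as the main measure. No document gives an SD for Ea or SVR by either method, so this cannot be shown.
- That the SVR error invalidates the comparison of groups. A constant factor does not.

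Two things survive. The printed SVR rule is wrong in its own unit. And the only formulas the protocol fixes sit under a test that part of the trial will not have. Reluctance to use Doppler stroke volume is also hard to sustain, since 14.2.5 already divides by it to obtain operant diastolic elastance.

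**Conclusion.** The SVR formula needs correcting. It understates SVR by exactly 1000 in dyne*sec/cm⁵, affecting reported values and raw differences but no test. This follows from the units printed in 14.2.4 and needs no assumption about patients.

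Adding echo-based Ea and SVR is a low-cost gain in coverage for a tertiary endpoint: atrial fibrillation patients, and patients at sites without MRI. The precision gain is modest, about 15–17% in standard error. It rests on equal SDs and equal missingness, and is gone if the echo SD is about 1.17–1.20 times the MRI SD. Coverage would improve even then. The primary and secondary analyses are untouched.

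**What to change.** - In 14.2.4, change SVR to 80 x MAP/(stroke volume in ml x heart rate/1000).
- In 14.2.5, add Ea = 0.9 x SBP/echo stroke volume (ml) and SVR = 80 x MAP/echo cardiac output (l/min), using the pressure and heart rate recorded at the echo. State the unit of cardiac output and one convention for MAP, common to both sections.
- Report the echo values in all patients alongside the MRI values in the MRI subset, without demoting MRI. Say in advance that both will be shown.
- Leave aortic thickness and distensibility on MRI.

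The cost is protocol wording and two derived variables from data already collected, with no new test or visit. The downside is that Doppler stroke volume may be noisier and the two methods may disagree in the subset that has both.

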14.2.5 Doppler echocardiography

A limited 2 D, M-mode and Doppler echocardiogram will be performed in each subject in the left lateral (parasternal long axis view and right ventricular (RV) inflow view) and the left lateral decubitus (apical 4 chamber and long axis views) positions using an appropriate echocardiographic instrument equipped with a multifrequency transducer as well as the Doppler tissue imaging (DTI) program. Blood pressure and heart rate will be recorded after the patient has acclimated to the imaging environment. In the parasternal long axis view, the diameter of left ventricular outflow tract (LVOT) will be measured just below the aortic valve. In the RV inflow view, guided by color flow imaging, continuous wave Doppler imaging will be used to measure the peak tricuspid regurgitant velocity. In the apical long axis view, pulsed wave Doppler echocardiography will be used to measure the LVOT velocity profile. In the apical 4-chamber view, the transmitral inflow velocity profile obtained from pulsed wave Doppler imaging at the tips of the mitral valve will be obtained. Doppler tissue imaging will be used to measure the septal and lateral mitral annular velocity in diastole. Guided by color flow imaging, continuous wave Doppler imaging will be used to measure the peak tricuspid regurgitant velocity. Measurements and derived values will be obtained in triplicate and measurements made at a core echocardiographic laboratory. Measurements and derived values include:

Stroke volume = $[3.14 \text{ x} (\text{LVOT diameter/2})^2]$ x time velocity integral of the pulsed wave LVOT velocity profile

Cardiac output = SV * heart rate

E velocity (cm/s) from the transmitral inflow velocity profile measured at leaflet tips.

E' velocity (cm/sec) (septal and lateral) from the diastolic mitral annular velocities measured with DTI. The E/E' ratio (septal and lateral) will be calculated for each subject.

Operant Ed will be calculated as (E/E')/stroke volume as previously reported ²⁷.

Peak pulmonary systolic pressure = $(4^{*}(\text{Peak TR velocity in m/sec})^{2} + 10)$ using the maximal TR velocity consistently measured (not following extrasystole)

Standardized image acquisition and measurement algorithms along with training materials will be provided to each participating center to enhance standardization of Doppler echocardiographic measurements.

14.2.6 Biomarker assays

All biomarker assays will be performed at a Core biomarker lab. cGMP and Aldosterone will be measured by RIA as previously described¹⁰¹. N-terminal pro BNP will be measured by the Roche assay as

previously described¹⁰². Plasma Amino-terminal propeptide of type III procollagen (PIIINP) levels have been shown to correlate with the extent of cardiac fibrosis in systolic HF and hypertensive heart disease and to reflect extracellular matrix metabolism, decreasing with therapies which reduce the degree of cardiac fibrosis and indices of LV diastolic dysfunction¹⁰³⁻¹¹⁰. Plasma PIIINP will be determined using a radioimmunoassay with a commercially available kit (Orion Diagnostica, Espoo, Finland). The intra-assay and interassay variations for determining PIIINP are 5.3% and 7.7%, respectively. The sensitivity (lower detection limit) is 0.2 μ g/L. Endothelin (marker of neurohumoral activation), troponin (marker of myocardial damage), uric acid (marker of oxidative stress) and cystatin C (marker of renal dysfunction) will also be measured.

